- In LT analysis, the ET and FU visits from BD/OLE Phase will be considered as “LTET” and “LTFU” visits. However, the LTET and LTFU visits will not be summarized in LT summary tables or figures.

3.8.3. Selection of Data in the Event of Multiple Records in an Analysis Visit Window

Depending on the statistical analysis method, single values may be required for each analysis window. For example, change from baseline by visit usually requires a single value, whereas a time-to-event analysis would not require 1 value per analysis window.

If multiple valid, nonmissing, continuous measurements exist in an analysis window, records will be chosen based on the following rules if a single value is needed:

- In general, the baseline value will be the last nonmissing value on or prior to the first dosing date of study drug in the corresponding study phase, unless specified differently. If multiple measurements occur on the same day, the last nonmissing value prior to the time of first dosing of study drug will be considered as the baseline value. If these multiple measurements occur at the same time or the time is not available, the average of these measurements (for continuous data) will be considered the baseline value.
- Baseline values of the liver tests (ALP, ALT, AST, and total bilirubin) in the BD Phase will be determined by averaging the values obtained at Screening and Baseline/Day 1. For the calculated baseline values, the reference range for each parameter will be defined as the one associated with the latest visit among all the values being averaged for each subject, for the purpose of determination of the abnormality and/or toxicity grades.
- For postbaseline values:
 - The record closest to the nominal day for that visit will be selected.
 - If there are 2 records that are equidistant from the nominal day, the later record will be selected.
 - If there is more than 1 record on the selected day, the average will be taken, unless otherwise specified.

If multiple valid, nonmissing, categorical measurements exist in an analysis window, records will be chosen based on the following rules if a single value is needed:

- For baseline, the last available record on or prior to the date of the first dose of study drug will be selected. If there are multiple records with the same time or no time recorded on the same day, the value with the lowest severity will be selected (eg, normal will be selected over abnormal for safety ECG findings).

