The tables will be repeated for the OLE Phase by treatment groups 5 – 8 in Section 3.2, except for height, fasting insulin, HOMA-IR, HbA1c, FibroScan, smoking status, diabetes diagnosis, IBD history and baseline classification of biliary tree disease due to PSC based on MRCP, which are not collected in the OLE Phase.

A by-subject listing of baseline characteristics will be provided by subject ID number in ascending order.

[figure not shown]

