- Change from baseline at each postbaseline visit

in the BD Phase, the OLE Phase and the LT analysis, separately.

A baseline laboratory value will be defined as the last measurement obtained on or prior to the date/time of first dose of study drug. Change from baseline to a postbaseline visit will be defined as the visit value minus the baseline value. The mean, median, Q1, Q3, minimum, and maximum

values will be displayed to the reported number of digits; SD values will be displayed to the reported number of digits plus 1.

Median (Q1, Q3) of the observed values for HOMA-IR, HbA1c, albumin, creatinine, fasting insulin, fasting glucose, prothrombin time, INR, WBC, neutrophils, lymphocytes, hemoglobin, platelets will be plotted using a line plot by treatment group and visit.

In the case of multiple values in an analysis window, data will be selected for analysis as described in Section 3.8.3.

7.2.2. **Graded Laboratory Values**

The CTCAE Version 4.03 will be used for assigning toxicity grades (0 to 4) to laboratory results for analysis. Grade 0 includes all values that do not meet the criteria for an abnormality of at least Grade 1. For laboratory tests with criteria for both increased and decreased levels, analyses for each direction (ie, increased, decreased) will be presented separately.

For the baseline ALP, ALT, AST, total bilirubin toxicity grades at the BD Phase, the CTCAE version 4.03 will be used to assign grades to the derived average values. See [Appendix 2](#) for the link to CTCAE 4.03.

7.2.2.1. **Treatment-Emergent Laboratory Abnormalities**

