7.2.3. Liver-related Laboratory Evaluations

Liver-related abnormalities after initial study drug dosing will be examined and summarized using the number and percentage of subjects who were reported to have the following laboratory test values for postbaseline measurements.

Subjects meet criteria for liver-related events:

- For subjects with normal baseline ALT (AST):
 - ALT (AST) $> 3 \times$ ULN
 - Total bilirubin $> 2 \times$ ULN
 - INR > 1.5 (except for subjects on anticoagulant therapy)
- For subjects with elevated ALT (AST) (\geq upper limit of normal [ULN]) at study start:
 - ALT (AST) $> 2 \times$ baseline
 - Total bilirubin $> 2 \times$ ULN
 - INR > 1.5 (except for subjects on anticoagulant therapy)

Subjects meet criteria for drug withheld:

- ALT (AST) $> 5 \times$ baseline
- ALT (AST) $> 10 \times$ ULN
- ALT (AST) $> 3 \times$ baseline with total bilirubin $> 2 \times$ ULN
- ALT (AST) $> 3 \times$ baseline with total bilirubin $> 1.5 \times$ baseline
- ALT (AST) $> 3 \times$ baseline with INR > 1.5 (except for subjects on anticoagulant therapy)
- ALT (AST) $>$ baseline with total bilirubin $> 2 \times$ ULN, and INR > 1.5 (except for subjects on anticoagulant therapy)
- ALT (AST) $>$ baseline with total bilirubin $> 1.5 \times$ baseline, and INR > 1.5 (except for subjects on anticoagulant therapy)

The summary will include data from all postbaseline visits up to 30 days after the last dose of study drug in the BD Phase (and on or before the first dose of the OLE Phase)/OLE Phase. LT analysis will include data summarized in BD Phase/OLE Phase. Data obtained after the last dose of study drug plus 30 days in the BD (and prior to first dose date of OLE Phase)/OLE Phase will not be included in the evaluation of the TE laboratory abnormalities in the LT analysis. For individual laboratory tests, subjects will be counted once based on the most severe postbaseline values. For the criteria of ALT (AST) and total bilirubin, INR, subjects will be counted once when the criteria are met at the same postbaseline visit date. The denominator is the number of subjects in the Safety Analysis Set/OLE Analysis Set who have nonmissing postbaseline values of all relevant tests at the same postbaseline visit date in the corresponding baseline group. A listing of subjects who met at least 1 of the above criteria will be provided.

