7.3. Vital Signs

Descriptive statistics will be provided for vital signs (systolic and diastolic blood pressure [mmHg], pulse [beats/min], respiratory rate [breath/min] and temperature [$^{\circ}$ C]) in the BD Phase, the OLE Phase and the LT analysis according to treatment groups in Section 3.2 as follows:

- Baseline value
- Values at each postbaseline visit
- Change from baseline at each postbaseline visit

A baseline value will be defined as the last available value collected on or prior to the date/time of first dose of study drug in the reporting phase. Change from baseline to a postbaseline visit will be defined as the postbaseline value minus the baseline value. Vital signs measured at unscheduled visits will be included for the baseline value selection.

In the case of multiple values in an analysis window, data will be selected for analysis as described in Section 3.8.3. No formal statistical testing is planned.

A by-subject listing of vital signs will be provided by subject ID number and visit in chronological order.

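### Can a subject fall into neither, or both, of the ALT (AST) groups in the open-label liver table?

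*SAP*

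**What the plan says.** Section 7.2.3 gives one set of liver criteria for the blinded (BD), open-label (OLE) and long-term (LT) summaries. The liver-related-event block has two parts. One is headed "For subjects with normal baseline ALT (AST"). The other is for subjects with ALT (AST) at or above the "upper limit of normal [ULN]) at study start". Study start is not defined anywhere in the SAP. The denominator is subjects with "nonmissing postbaseline values of all relevant tests at the same postbaseline visit date in the corresponding baseline group". A second block, the drug-withheld criteria, is not split by group; six of its seven rows use a multiple of baseline or a rise above it. For the long-term table the section says only that "LT analysis will include data summarized in BD Phase/OLE Phase".

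On what baseline means:

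- Section 3.8.3 sets the general rule: the last nonmissing value "on or prior to the first dosing date of study drug in the corresponding study phase, unless specified differently". In the BD Phase only, ALT, AST, ALP and total bilirubin use the average of Screening and Day 1.
- Table 3-5 in Section 3.8.2 defines an OLE Baseline for chemistry and coagulation tests.
- Section 5.2 classifies baseline ALT and AST as below ULN or at/above ULN, then adds "The tables will be repeated for the OLE Phase by treatment groups" 5 to 8. ALT and AST are not among the listed exceptions.
- Section 7.2.1 names no phase: "A baseline laboratory value will be defined as the last measurement obtained on or prior to the date/time of first dose of study drug". Section 7.3, for vital signs, does: "on or prior to the date/time of first dose of study drug in the reporting phase".

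**The concern.** The two labels look like two halves of one split, but they use different time words. In the OLE table the words can point to different dates: OLE baseline under the Section 3.8.3 default, and the start of the blinded phase under the ordinary meaning of study start. A subject normal at study start and elevated at OLE entry would then meet neither heading. A subject elevated at study start and normal at OLE entry would meet both, with two criteria and two denominators.

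Safety is the primary objective, and the subjects left out would be those whose ALT or AST had risen above the ULN. For OLE groups 5 and 6 the interval includes 12 weeks of active treatment. The bilirubin and INR rows of the event block sit under the same two headings, so they would drop out too. Separately, if two programmers chose different baselines, the same OLE sample could be counted differently.

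**Working it through.** The plan gives no figure here to reproduce, so the check is one of classification.

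**Step 1: enumerate.** Take an illustrative ULN of 40 and ALT of 30, 40 or 60 at BD baseline and at OLE baseline, giving 3 × 3 = 9 combinations. Normal means below ULN; elevated means at or above it.

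| Reading of the two labels in the OLE table | Neither | Both | Exactly one |
|---|---|---|---|
| Mixed: normal at OLE baseline, elevated at BD start | 2 | 2 | 5 |
| Both at OLE baseline | 0 | 0 | 9 |
| Both at BD baseline | 0 | 0 | 9 |

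Under the mixed reading the *neither* cases are BD 30 with OLE 40 or 60; the *both* cases are BD 40 or 60 with OLE 30. Either consistent reading removes the problem entirely.

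**Step 2: size under the mixed reading only.** The SAP gives no ALT distribution, so these inputs are assumptions: median ALT 1.0 to 2.0 × ULN, between-subject SD of log ALT 0.5 to 0.8, within-subject CV 15% to 30%, no drug effect. BD baseline is the mean of two values, OLE baseline is one value. By simulation:

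| Setting (median, SD, CV) | Neither | Both | Total | Of 50 |
|---|---|---|---|---|
| Lowest (2.0, 0.5, 15%) | 2.0% | 2.6% | about 4.5% | 2.3 |
| Middle (1.5, 0.8, 30%) | 5.3–5.4% | 6.8% | about 12% | 6.1 |
| Highest (1.0, 0.5, 30%) | 9.6% | 11.2% | about 21% | 10.4 |

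Fifty is the planned total (20 + 20 + 10) and so the ceiling for OLE entry.

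**Step 3: does Section 7.2.3 support the mixed reading?**

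- Its denominator sentence speaks of the corresponding *baseline* group for both halves. A group fixed at some other time would not be a baseline group.
- The elevated group's own criterion is ALT (AST) above 2 × *baseline*. It would be odd to select subjects at one time and scale their threshold at another.
- Section 5.2 already tabulates the matching pair, below ULN and at/above ULN, at OLE baseline.

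**Step 4: test the literal reading on the BD table.** If study start literally meant the Day 1 value, the BD table would break too, because BD baseline ALT and AST average Screening and Day 1. Under the Step 2 assumptions, 1.6% to 6.6% of subjects would be in neither BD group and 1.0% to 5.1% in both. The sensible reading is that study start is a loose synonym for baseline.

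**Step 5: which baseline in the OLE table?** This does affect the thresholds. For ALT of 1.2 × ULN at BD baseline and 2.0 × ULN at OLE baseline, 2 × baseline is 2.4 or 4.0 × ULN. Section 3.8.3 supplies a default, the baseline of the corresponding phase, and Table 3-5 supplies the OLE Baseline window for these tests. Section 7.2.1 names no phase, but its definition serves summaries produced separately for the BD Phase, the OLE Phase and the LT analysis, and ALT and AST are not among its listed analytes. Nothing in Section 7.2.3 sets the default aside apart from the loose label.

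**The case for a change.** The strongest contrary case is that study start is undefined in a table serving the primary objective, and that calling it a synonym for baseline does not say *which* baseline the OLE table uses. Other safety sections differ: vital signs use the reporting phase, partial Mayo score uses the BD Phase, and the laboratory definition names none. Groups of at most 20, 20 and 10 are small enough for a few reclassified subjects to move a percentage visibly. The by-subject listing covers only subjects who met a criterion, so it would not recover someone to whom no event criterion was applied, unless that subject met a drug-withheld row.

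Part of this stands. The term is undefined, the LT table is looser than the OLE table, and the reference to a baseline group has no meaning for the unsplit drug-withheld rows.

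It does not carry the main claim. Variation between other sections does not displace the Section 3.8.3 default, and partial Mayo score has its own explicit rule. The baseline-group wording naturally applies only where there are groups. Even under the mixed reading, a subject in neither group is still assessed on all seven drug-withheld rows and in the CTCAE-graded summaries of Section 7.2.2, which take every subject with postbaseline values. The interval to OLE entry also includes a planned gap of about 4 weeks off drug (Appendix 1, footnote c).

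**Conclusion.** The mismatch in wording is real, but the feared result is not what the plan prescribes. Subjects fall in neither group or both only if one table mixes two time points, and the 2 to 10 subjects out of 50 rest on that reading plus assumed ALT distributions and full OLE entry. With a single time point the number is zero. What remains is an imprecise label and an unstated choice of phase, for which Section 3.8.3 gives a default. An analyst would apply one baseline to both groups when programming the table; writing that down records the choice without improving the method. The table is descriptive, so no test or error rate is affected. No change to the plan is needed. This says nothing about whether any liver threshold or drug-withholding rule is clinically right.

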7.3. Vital Signs

Descriptive statistics will be provided for vital signs (systolic and diastolic blood pressure [mmHg], pulse [beats/min], respiratory rate [breath/min] and temperature [$^{\circ}$ C]) in the BD Phase, the OLE Phase and the LT analysis according to treatment groups in Section 3.2 as follows:

- Baseline value
- Values at each postbaseline visit
- Change from baseline at each postbaseline visit

A baseline value will be defined as the last available value collected on or prior to the date/time of first dose of study drug in the reporting phase. Change from baseline to a postbaseline visit will be defined as the postbaseline value minus the baseline value. Vital signs measured at unscheduled visits will be included for the baseline value selection.

In the case of multiple values in an analysis window, data will be selected for analysis as described in Section 3.8.3. No formal statistical testing is planned.

A by-subject listing of vital signs will be provided by subject ID number and visit in chronological order.

7.4. Prior and Concomitant Medications

Medications collected at screening and during the study will be coded using the current version of the World Health Organization (WHO) Drug dictionary.

7.4.1. Prior Medications

Prior medications are defined as any medications taken before a subject took the first study drug.

Prior medications will be summarized by preferred name using the number and percentage of subjects for each treatment group and overall in BD Phase. A subject reporting the same medication more than once will be counted only once when calculating the number and percentage of subjects who received that medication. The summary will be ordered by preferred term in order of descending overall frequency. For drugs with the same frequency, sorting will be done alphabetically.

For the purposes of analysis, any medication with a start date prior to the first dose date of study drug will be included in the prior medication summary regardless of when the stop date is. If a partial start date is entered the medication will be considered prior unless the month and year (if day is missing) or year (if day and month are missing) of the start date are after the first dose date. Medications with a completely missing start date will be included in the prior medication summary, unless otherwise specified.

Summaries will be based on the Safety Analysis Set. No formal statistical testing is planned.

7.4.2. Concomitant Medications

Concomitant medications are defined as medications taken while a subject took study drug. Use of concomitant medications will be summarized by preferred name using the number and percentage of subjects for each treatment group. A subject reporting the same medication more than once will be counted only once when calculating the number and percentage of subjects who received that medication. The summary will be ordered by preferred term in descending frequency in the GS-9674 100 mg group (BD Phase/LT analysis), and in the GS-9674 Total group (OLE Phase). For drugs with the same frequency, sorting will be done alphabetically.

For the purposes of analysis, any medications with a start date prior to or on the first dose date of study drug of the study phase and continued to be taken after the first dose date, or started after the first dose date but prior to or on the last dose date of study drug of the study phase will be considered concomitant medications. Medications started and stopped on the same day as the first dose date or the last dose date of study drug will also be considered concomitant.

Medications with a stop date prior to the date of first dose date of study drug or a start date after

the last dose date of study drug will be excluded from the concomitant medication summary. If a partial stop date is entered, any medication with the month and year (if day is missing) or year (if day and month are missing) prior to the date of first study drug administration will be excluded from the concomitant medication summary. If a partial start date is entered, any medication with the month and year (if day is missing) or year (if day and month are missing) after the study drug stop date will be excluded from the concomitant medication summary. Medications with completely missing start and stop dates will be included in the concomitant medication summary, unless otherwise specified. Summaries will be based on the Safety Analysis Set/OLE Analysis Set. No formal statistical testing is planned.

All prior and concomitant medications (other than per-protocol study drugs) will be provided in a by-subject listing sorted by subject ID number and administration date in chronological order.

7.5. Electrocardiogram Results

ECG analysis results are intended to identify meaningful abnormalities. If potential abnormalities of interest are identified, further analyses may be conducted.

A shift table of the investigators' assessment of ECG results at Week 12 of the BD Phase compared with baseline values will be presented by treatment group using the following categories: normal; abnormal, not clinically significant; abnormal, clinically significant; or missing. The number and percentage of subjects in each cross-classification group of the shift table will be presented. Subjects with a missing value at baseline or postbaseline will not be included in the denominator for percentage calculation. No formal statistical testing is planned.

A by-subject listing for ECG assessment results will be provided by subject ID number and visit in chronological order.

7.6. Other Safety Measures

7.6.1. Partial Mayo Score

The partial Mayo score is a survey score for the assessment of IBD that considers stool frequency and rectal bleeding. At each study visit, two sub score components will be reported:

- Stool frequency sub score: a numeric value ranging from 0 to 3 (where 0 = normal for the patient, 1 = 1 – 2 stools more than normal, 2 = 3 – 4 stools more than normal, 3 = 5 or more stools more than normal);
- Rectal bleeding sub score: a numeric value ranging from 0 to 3 (where 0 = no blood seen, 1 = streaks of blood with stool less than half the time, 2 = obvious blood with stool most of the time, 3 = blood alone passes).

Partial Mayo score will be calculated as the sum of the above two sub scores. If one or both sub scores are missing, partial Mayo score will be considered missing.

Partial Mayo score and its two components will be reported for subjects with IBD history based on the Safety Analysis Set for the BD Phase, and the LT analysis. Partial Mayo score in the OLE Phase will be summarized based on the OLE Analysis Set.

Descriptive statistics will be provided for partial Mayo score in the BD Phase, the OLE Phase and the LT analysis according to treatment groups in Section [3.2](#) as follows:

- Baseline value
- Values at each postbaseline visit
- Change from baseline at each postbaseline visit

A baseline value will be defined as the last available value collected on or prior to the date/time of first dose of study drug in the BD Phase. Change from baseline to a postbaseline visit will be defined as the postbaseline value minus the baseline value. Partial Mayo scores calculated at unscheduled visits will be included for the baseline value selection.

For each subject, the nadir will be determined as the minimum score from baseline to the last available visit; change from nadir will be calculated only for visits that are after the earliest visit with the nadir value. Nadir values will be summarized using descriptive statistics.

Subjects with change from nadir at any visit \geq 2 points and within 30 days of the last dose in each phase will be identified. Number and percent of these subjects will be reported. Maximum change from nadir for these subjects will be summarized.

In the case of multiple values in an analysis window, data will be selected for analysis as described in Section [3.8.3](#). No formal statistical testing is planned.

A by-subject listing of available partial Mayo scores, its two components, nadir and change from nadir will be provided by subject ID number and visit in chronological order. Any subject with a history of IBD who experiences at least a 2-point increase from nadir in the partial Mayo score during the course of the study within 30 days of the last dose will be flagged in the listing.

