3.2. Subject Grouping

For analyses based on the FAS, subjects will be grouped according to the treatment to which they were randomized. For analyses based on the Safety Analysis Set and PK Analysis Set, subjects will be grouped according to actual treatment received. The actual treatment received will differ from the randomized treatment only when their actual treatment differs from randomized treatment for the entire treatment duration in the BD Phase.

For analyses in the BD Phase, subjects will be grouped into the following groups, and only the BD Phase data will be summarized:

- 1) BD Phase GS-9674 100 mg: This group includes all subjects who were on GS-9674 100 mg in the BD Phase;
- 2) BD Phase GS-9674 30 mg: This group includes all subjects who were on GS-9674 30 mg in the BD Phase;
- 3) BD Phase GS-9674 Pooled: This group includes all subjects who were on GS-9674 100 mg or GS-9674 30 mg in the BD Phase;
- 4) BD Phase Placebo: This group includes all subjects who were on Placebo in the BD Phase.

Treatment groups 1, 2, and 4 will be presented in efficacy tables in BD Phase. Treatment groups 1 - 4 will be presented in all tables other than efficacy tables in BD Phase.

For analyses in the OLE Phase, subjects will be grouped into the following groups, and only the OLE Phase data will be summarized:

- 5) OLE Phase GS-9674 - Previously in 100 mg: This group includes all subjects who received the OLE study drug and previously received GS-9674 100 mg in the BD Phase;
- 6) OLE Phase GS-9674 - Previously in 30 mg: This group includes all subjects who received the OLE study drug and previously received GS-9674 30 mg in the BD Phase;
- 7) OLE Phase GS-9674 - Previously in Placebo: This group includes all subjects who received the OLE study drug and previously received placebo in the BD Phase;
- 8) OLE Phase GS-9674 Total: This group includes all subjects who received the OLE study drug.

For long-term (LT) analyses, subjects will be grouped into the following groups, and data from both BD Phase and OLE Phase will be summarized:

- 9) LT GS-9674 initially in 100 mg: This group includes all subjects who received GS-9674 100 mg in the BD Phase and may or may not enter the OLE Phase;
- 10) LT GS-9674 initially in 30 mg: This group includes all subjects who received GS-9674 30 mg in the BD Phase and may or may not enter the OLE Phase.

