3.8.2. Analysis Visit Windows

Subject visits might not occur on protocol-specified days. Therefore, for the purpose of analysis, observations will be assigned to analysis windows.

The analysis windows to be applied to the BD Phase are provided in [Table 3-1](#), [Table 3-2](#), [Table 3-3](#) and [Table 3-4](#), except that the algorithm for assigning baseline analysis window does not apply to the liver tests (ALP, ALT, AST, and total bilirubin). For these 4 parameters, the baseline values will be determined by averaging the values obtained at screening and Baseline/Day 1, and no specific study day is associated with the average values.

Table 3-1. Analysis Visit Windows in BD Phase for Partial Mayo Score, Vital Signs, Body Weight, Pruritus Measures, Chemistry, Hematology, Coagulation Laboratory, and Mayo Risk Score

Analysis Visit	Study Day	Lower Limit	Upper Limit
Baseline	1	NA	1
Week 1	8	2	11
Week 2	15	12	21
Week 4	29	22	42
Week 8	57	43	70
Week 12	85	71	≥ 85

NA = not applicable

Table 3-2. Analysis Visit Windows in BD Phase for Lipid Profiles and Pooled Cohort Risk Score

Analysis Visit	Study Day	Lower Limit	Upper Limit
Baseline	1	NA	1
Week 1	8	2	18
Week 4	29	19	42
Week 8	57	43	70
Week 12	85	71	≥ 85

NA = not applicable

Table 3-3. Analysis Visit Windows in BD Phase for Fibroscan®, QoL Questionnaires, and Electrocardiogram (ECG), HOMA-IR, HbA1c, C-peptide, Insulin, ELF™ Score, FibroSURE/FibroTest, High-sensitivity C-reactive Protein (hsCRP)

Analysis Visit	Study Day	Lower Limit	Upper Limit
Baseline	1	NA	1
Week 12	85	2	≥ 85

NA = not applicable

Table 3-4. Analysis Visit Windows in BD Phase for FGF19, C4 and Total Bile Acids

Analysis Visit	Study Day	Lower Limit	Upper Limit
Baseline	1	NA	1
Week 1	8	2	18
Week 4	29	19	56
Week 12	85	57	≥ 85

NA = not applicable

The analysis windows to be applied to the OLE Phases are provided in [Table 3-5](#), [Table 3-6](#), [Table 3-7](#), [Table 3-8](#), [Table 3-9](#) and [Table 3-10](#).

Table 3-5. **Analysis Visit Windows in OLE Phase for Partial Mayo Score, Vital Signs, Body Weight, Lipid Profiles, Pruritus Measures, Chemistry, Hematology, Coagulation Laboratory, Pooled Cohort Risk Score and Mayo Risk Score**

Analysis Visit	OLE Study Day	Lower Limit	Upper Limit
OLE Baseline	1	NA	1
OLE Week 1	8	2	11
OLE Week 2	15	12	21
OLE Week 4	29	22	42
OLE Week 8	57	43	70
OLE Week 12	85	71	126
OLE Week 24	169	127	210
OLE Week 36	253	211	294
OLE Week 48	337	295	378
OLE Week 60	421	379	462
OLE Week 72	505	463	546

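### In the OLE tables, partial Mayo change from baseline is measured from the BD Phase baseline, so it mixes change on open-label drug with change that came before it

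*SAP*

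**What the plan says.** Section 7.6.1 sets the scope: "Descriptive statistics will be provided for partial Mayo score in the BD Phase, the OLE Phase and the LT analysis", each with baseline value, visit values and change from baseline. It then defines baseline once, as the last available value "on or prior to the date/time of first dose of study drug in the BD Phase". No separate rule is given for the OLE tables.

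Four other places in the SAP bear on this:

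- Section 3.8.3 makes the baseline, by default, the last value up to the first dose of the corresponding phase, but gives way where another rule is stated. Section 7.6.1 states another rule, so it governs.
- Section 3.8.2, Table 3-5 ("Analysis Visit Windows in OLE Phase for Partial Mayo Score" and other measures) includes an OLE Baseline row at OLE study day 1.
- Section 5.2 lists baseline partial Mayo score among the baseline characteristics and repeats those tables for groups 5–8. It leaves out only items not collected in the OLE Phase, and partial Mayo is not among them.
- Section 7.3, which is built almost identically, takes the vital-signs baseline "on or prior to the date/time of first dose of study drug in the reporting phase".

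For groups 5–8, section 3.2 adds that "only the OLE Phase data will be summarized".

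On the nadir, section 7.6.1 says that for each subject "the nadir will be determined as the minimum score from baseline to the last available visit". Subjects who rise 2 or more points above it "and within 30 days of the last dose in each phase will be identified".

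**The concern.** The OLE Phase has no concurrent control, so the reference value decides what is read as change on open-label GS-9674. OLE dosing starts only after 12 weeks of blinded treatment and a follow-up visit about 4 weeks after the last blinded dose (section 1.2; Appendix 1, footnote c). With the BD baseline as reference, an OLE column contains three things added together: change on blinded treatment, change off drug and change on open-label drug. For group 7 the first of these is change on placebo. For groups 5 and 6 it is change on blinded active drug.

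There is also a labelling problem. The section 5.2 table repeated for groups 5–8 appears to call for an OLE-entry value of partial Mayo, while the section 7.6.1 OLE table would print the BD value as baseline. The same subjects could then carry two different baselines in the OLE outputs.

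**Working it through.** The SAP gives no figure on this point, so there is nothing to reproduce. The check applies the section 7.6.1 rules literally to example score paths and compares them with a reporting-phase baseline.

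**Inputs**

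- Post-baseline OLE visits in Table 3-5: Weeks 1, 2, 4, 8, 12, 24, 36, 48, 60, 72, 84 and 96, which is 12 visits.
- Placebo arm: n = 10 (section 1.2), an upper bound for group 7. Section 7.6.1 reports only subjects with IBD history, so the number contributing may be smaller.
- The scores below are assumed, for illustration only.

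**Identity**

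Change from BD baseline = change from OLE Baseline + (OLE Baseline − BD baseline). The bracket is the part that arose before open-label treatment, and it can have either sign.

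**Example paths**

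| Path | BD baseline | OLE Baseline | OLE visits | Change as written | Change from OLE Baseline |
|---|---|---|---|---|---|
| A: rises on placebo, then flat | 0 | 2 | 2 at all 12 | +2 at all 12 | 0 at all 12 |
| B: rises only in the off-drug gap, then flat | 0 | 2 | 2 at all 12 | +2 at all 12 | 0 at all 12 |
| C: falls in the BD Phase, returns in OLE | 2 | 0 | 0, 1, then 2 at ten | −2, −1, then 0 at ten | 0, +1, then +2 at ten |

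Paths A and B show worsening that did not occur on open-label drug. Path C hides a 2-point worsening that did.

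**Group level**

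Suppose k of n contributing group 7 subjects follow path A or B and the rest do not change. The OLE mean change as written is 2k/n. Measured from OLE Baseline it is 0.

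- n = 10: k = 1, 2, 3, 5 gives 0.2, 0.4, 0.6, 1.0 points.
- n = 6 (an assumed number with IBD history): k = 1 gives 2/6 = 0.33 points.

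**Nadir count on the same paths**

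- A and B: the study-wide nadir is 0, so the rise during OLE is 2 and the subject is counted in the OLE Phase. With a nadir taken from OLE Baseline onward the rise is 0 and the subject is not counted. One such subject is 1/10 = 10% of group 7 at n = 10, or 1/6 = 17% at n = 6.
- C: the nadir is 0 and the maximum rise is 2 under either definition, so the nadir count catches the worsening that change from baseline misses.

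The words about each phase limit when a rise is counted. They do not restart the nadir. A rise that begins on placebo and persists, as in path A, can therefore be counted under placebo in the BD Phase and again under GS-9674 in the OLE Phase.

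**The case against.** The best defence is that section 7.6.1 is an explicit choice and section 3.8.3 permits it. A pre-treatment reference is reasonable for an IBD safety score, and OLE Day 1, coming after blinded treatment and a drug-free interval, is not a clean baseline either. Section 3.2 controls which observations enter the OLE tables and need not control the value they are compared with. The SAP also maps the BD baseline MRE to OLE Baseline. Finally, group 7 is labelled as previously on placebo, the BD tables show the placebo period, and a by-subject listing shows every score.

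Much of this stands. Section 3.2 alone does not settle the matter, the analysis is descriptive, and the listing lets a careful reader recover each path. But the MRE parallel is weak, because MRE is not collected at OLE Day 1 whereas partial Mayo is. The case for a pre-treatment reference is already met by the LT analysis for groups 9–10. Permission to depart from a default is not a reason to do so where Table 3-5, section 5.2 and section 7.3 all point to the phase-specific value.

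A reader might infer three stronger points, which the SAP does not support:

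- *The nadir is wrongly defined and must restart at OLE entry.* It is defined once per subject up to the last visit, and the listing flag covers the whole course of the study. A study-wide nadir looks intended, and it is the more sensitive screen. Only its label in the OLE table needs attention.
- *The laboratory baseline has the same fault.* Section 7.2.1 says "A baseline laboratory value will be defined as the last measurement obtained on or prior to the date/time of first dose of study drug" and names no phase, so the section 3.8.3 default supplies it.
- *The primary objective is compromised.* Section 1.1 states general safety and tolerability and does not name IBD. Partial Mayo is placed under other safety measures.

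**Conclusion.** The point holds for change from baseline in the OLE tables. As written, that change is the open-label change plus a carried-over term from blinded treatment and the off-drug gap, and the reference conflicts with the OLE Baseline that the SAP itself sets up for this score.

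It would be tempting to conclude that the tables will blame open-label GS-9674 for worsening on placebo. The SAP does not support a one-sided claim: path C shows the same rule hiding worsening, and for groups 5 and 6 the carried-over term comes from active treatment. The size is unknown, because the number with IBD history, the number entering the OLE Phase and the score distribution are not given. The worked figures (0.2 points of mean change and 10% in the nadir count per affected subject at n = 10) rest on assumed paths and on the upper bound for group 7. They show sensitivity in a small group and do not predict a result.

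The correction is worth making because it is cheap and removes an ambiguity in an uncontrolled phase.

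**What to change.** In section 7.6.1:

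1. For the OLE tables, define baseline as the last value on or before the first dose of the reporting phase, as section 7.3 does. Keep the BD baseline for the BD and LT analyses.
2. Keep the study-wide nadir and the listing flag. Label the OLE count of rises of 2 or more points as measured from a study-wide nadir. Optionally, add a count of subjects whose rise of 2 or more points occurred after OLE Baseline.

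Section 7.2.1 needs no change.

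**Cost:** a wording change and one programming rule. Appendix 1 already schedules partial Mayo at OLE Baseline/Day 1, so no new data are needed. The downside is that whole-study change for former placebo subjects leaves the OLE table and has no place in the LT tables, because groups 9–10 exclude them. The by-subject listing still shows their scores in order.
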